16.3 Missing, unused & spurious data

Detail provided in the Statistical Analysis Plan (SAP).

16.4 Procedures for reporting deviation(s) from the original SAP

These will be submitted as substantial amendments where applicable and recorded in subsequent versions of the protocol and SAP.

16.5 Termination of the trial

Two interim analyses after 77 and 115 events (600-760 randomized) would trigger early stopping if the log-rank statistic is larger than +/- 3.36 and +/- 2.68 respectively. Stopping for efficacy means fewer participants and shorter follow-up. Otherwise, the trial will be analyzed when at least 194 events have been reported.

16.6 Inclusion in analysis

All randomised participants will be included in the Intention-to-treat (ITT) analysis of the primary endpoint. Full details will be provided in the SAP. In general, a treatment policy approach to estimands will be used to deal with intercurrent events such as adverse events and discontinuation of treatment. Patients that withdraw completely or are lost to follow-up will be censored at the date last known to be recurrence free and patients that die due to other causes will be censored at the time of death. Full details on the estimand framework and handling of missing data will be provided in the SAP.

17 Analysis

17.1 Main analysis

The trial will be analysed when at least 194 events have been reported.

Patients that withdraw completely or are lost to follow-up will be censored at the date last known to be recurrence free and patients that die due to other causes will be censored at the time of death.

A full statistical analysis plan will be finalised prior to the first formal analysis of this group sequential trial. The primary analysis is the stratified logrank test. The design will include two formal interim analyses after 77 and 115 events (appx. 600 and 760 randomised), allowing the trial to stop early if, at each formal interim analysis the log-rank test statistic is larger than +/- 3.36 and +/- 2.68 respectively. Stopping for efficacy at either interim analysis would mean fewer participants need to be recruited and follow-up can be reduced for the remaining patients. If the test statistic is not large enough at the interim analyses, the trial will continue to the full target, and will be analysed when at least 194 events have been reported. The log-rank test will be significant if the final test statistic is greater +/- 1.98 (45). The total alpha spent in all 3 analyses adds up to 5%. We will actively monitor recruitment (LRR event rates, dropout rates) to project when the necessary number of events might occur. This will allow timely recruitment adjustments if needed. Recruitment projections are based on 100 patients in year 1, 200 in year 2, 240 in year 3 and 300 in year 4. Alternative study lengths and recruitment periods were considered; this was found to be the most realistic in ensuring recruitment to the required sample size in the shortest overall duration.

If proportional hazards assumptions are not violated, then a Cox regression model will be used to estimate the hazard ratio for the primary outcome and for secondary outcomes of distant metastasis-free survival and overall survival, adjusted for prognostic factors. If the proportional hazards model is strongly violated, then restricted mean survival analysis methodology will be used for multivariable analysis.

17.2 Interim analysis

Internal Pilot or feasibility studies progression criteria. Proposed length of internal pilot phase: 18 months (12 months from opening to recruitment).

An internal pilot targeting recruitment of 100 patients within the first 12 months will determine feasibility. Recruitment prediction is based on site interest and experience on speed of site opening.

In our MDT survey, >90% of MDTs discussed 5 or more HR-cSCC patients per month and 25% discussed >15, which is in line with the published incidence of HR-cSCC (7). The average predicted recruitment from the 25 centres was 2-3 patients per month. We will use a traffic light system to determine feasibility and have developed a recruitment prediction based on the recently obtained expressions

of interest (EOIs) and experience on speed of centre opening. This takes a very conservative approach having taken a quarter of the expected recruitment received in the EOIs from centres, with additional reduction of outliers. The population served by the MDT was taken into consideration for further adjustment. The figures shown in the table 5 below would be at the timepoint 12 month from opening the first site.

Table 6. Traffic light feasibility

	Red	Amber	Green
Number of centres open	<8	Between 8 and 15	>15
Latest monthly recruitment	<10	Between 10 and 16	>16
Total number of patients recruited	<50	Between 50 and 100	>100

Two interim analyses after 77 and 115 events (600-760 randomised) trigger early stopping if the log-rank statistic is larger than +/- 3.36 and +/- 2.68 respectively. Stopping for efficacy means fewer participants and shorter follow-up.

17.3 Quality of Life (QoL)

QoL improvement will be assessed primarily using the global health status derived from the EORTC QLQ-C30 questionnaire at 4 months from baseline (change from baseline in global health status score) between the two arms. This will be calculated as per scoring instructions in the EORTC QLQ-C30 manual. For analyses, descriptive statistics will be produced, using medians and interquartile ranges (IQRs) instead of means and standard deviations in cases of heavily skewed data. The standardized Skin Cancer Index questionnaire will be analysed, and missing data handled in accordance with their respective guidelines. Proportion of patients experiencing a change from baseline for each measure as well as mean group changes will be calculated. Associations between the reporting of skin toxicity due to radiotherapy between clinicians and patients (using CTCAE, v5.0) at the same timepoints will be explored. In addition, sub-group analyses based on age, gender, treatment arm, will be undertaken. Statistical significance tests will be carried out if clinically significant differences are observed. Independent samples t-tests will be used to compare means, and the nonparametric equivalent will be used to compare medians in the case of skewed data. Proportions will be compared using the chi-square test. Associations will be explored using multivariate regression analyses if sample size allows.

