5.2 Secondary objectives

- To determine the impact on QoL of ART in completely resected high risk (BWH T2b/3) primary cSCC compared to standard clinical follow up.
- To evaluate distant metastasis-free survival in both groups.
- To evaluate overall survival (OS) in both groups.
- To determine the safety of ART in terms of the proportion of patients experiencing toxicity compared with close clinical follow up.
- To evaluate the cost-effectiveness of ART.

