16.2 Sample size

Assuming a conservative LRR of 20% for T2b and 50% for T3 cSCC (16, 17), and UK data confirm 92% of recurrence is within 3 years (14). Our extensive SSMDT and PPI work support a 35% reduction as a meaningful clinical effect in LRR as justification for use of ART (26, 27). This plausibility of this effect size is also supported by a recently published observational study (24). For the primary outcome to improve LRR-free survival from the current rate of 80% to 87% at 3 years (reduction in LRR events of 35%) translates into a hazard ratio of 0.624. In absolute terms, for a LRR of 20 out of 100 recurrences, 35% reduction translates to 7 fewer recurrences.

The sample size was calculated based on the time-to event outcome of LRR free survival, using the armenu package in Stata 17. With the expected 3-year LRR-free survival of 0.8 in the standard clinical

follow up arm, and a HR of 0.624, with 1:1 allocation ratio and applying a two-sided type I error rate of 5% and 90% power, 194 events are required for analysis of the primary outcome. Recruiting 752 patients over 4 years with these assumptions predicts that this number of events will be observed after approximately 3 years follow-up. Allowing for 10% dropouts (loss to follow up, withdrawals, deaths from other causes – all censored observations), and rounding up slightly, the total sample size required is 840 patients.

We will use competing risks regression to account for death from other causes or distant metastasis events prior to local recurrence. Because most of these events will be due to death from other causes rather than distant metastases, we do not expect this to be more than the 10% we have allowed for attrition. However, if competing events are seen to be higher than expected during trial monitoring, we will discuss with the funders about the possibility of recruiting more patients to achieve the target number of LRR events.

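### The quality-of-life arms are formally compared only if a clinically significant difference is first observed, so a smaller real difference gets no formal inference; the t-test on change is valid but less efficient than baseline adjustment

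*Protocol*

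**What the plan says.** Quality of life is a comparative secondary objective in section 5.2: "To determine the impact on QoL of ART in completely resected high risk (BWH T2b/3) primary cSCC compared to standard clinical follow up". Section 17.3 fixes the main measure, "QoL improvement will be assessed primarily using the global health status derived from the EORTC QLQ-C30 questionnaire", and the contrast, "at 4 months from baseline (change from baseline in global health status score) between the two arms".

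The section promises descriptive statistics without condition: means with standard deviations (medians with interquartile ranges if heavily skewed), mean group changes, and the proportion of patients who change. Formal testing is conditional: "Statistical significance tests will be carried out if clinically significant differences are observed". The method then named is "Independent samples t-tests will be used to compare means", with a nonparametric equivalent for skewed data and chi-square for proportions. Regression appears once, for another purpose: "Associations will be explored using multivariate regression analyses if sample size allows".

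The section gives no threshold for clinical significance and mentions no confidence interval for the arm difference. Table 2 schedules the QLQ-C30 at baseline and at 4 months in both arms.

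**The concern.** Whether formal inference is made on a stated objective depends on the size of the observed difference. Two things follow.

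- A real difference below the threshold is not tested, however precisely it is measured. The report then has no formal statement to separate little or no effect from a modest real one.
- A difference singled out because it crossed the threshold is, on average, larger than the truth.

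This matters here because the lay summary (section 3.3) expects short-term skin inflammation from radiotherapy and says its use should stop if it is ineffective or has too many side effects. A modest quality-of-life deficit at 4 months is therefore a result that readers will want.

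The protocol treats comparable outcomes differently. Section 17.1 gives distant metastasis-free and overall survival an adjusted Cox model with no condition on the observed effect. Section 17.5 corrects EQ-5D-5L utilities for baseline imbalance by regression. Section 17.3 does neither for the QLQ-C30 arm comparison.

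**Working it through.** **The plan's own figures.** The protocol gives no sample size or power for quality of life; "applying a two-sided type I error rate of 5% and 90% power, 194 events are required" concerns the primary outcome only. The total reproduces: 752 / 0.9 = 835.6, so 836, rounded up to 840. Less 10%, this leaves 756 patients, or 378 per arm.

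**Assumptions (not in the protocol).** SD of the change score 20 to 25 points; 378 per arm, or 350 if more 4-month questionnaires are missing; threshold of 3, 4, 5 or 10 points; true deficit of 5 points.

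**Precision.** SE = SD × √(2/n), and the two-sided 5% limit is 1.96 × SE. Power with no threshold is Φ(5/SE − 1.96).

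| n per arm | SD | SE | Significant above | Power, no threshold |
|---|---|---|---|---|
| 350 | 20 | 1.51 | 2.96 | 91% |
| 350 | 25 | 1.89 | 3.70 | 75% |
| 378 | 20 | 1.45 | 2.85 | 93% |
| 378 | 25 | 1.82 | 3.56 | 79% |

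**With a threshold g.** A significant test requires the observed difference to exceed both g and the limit above, so the probability is Φ((5 − max(g, limit))/SE).

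- g = 10: Φ(−5/SE) = 0.03% to 0.4%.
- g = 5: Φ(0) = 50%, because the threshold equals the true value.
- g = 4: Φ(1/SE) = 70% to 75%.
- g = 3: 75% to 92%, within about 1.5 percentage points of the power with no threshold.

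**When the threshold is passed.** An observed 5-point difference already has z = 5/SE = 2.6 to 3.4, and a 10-point one z = 5.3 to 6.9. Under these assumptions, a result that passes is significant by construction and the test adds nothing.

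**Exaggeration.** With a true 5-point difference, results passing a 5-point threshold average 5 + 0.798 × SE = 6.2 to 6.5 points. Results passing a 10-point threshold are at least twice the truth.

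**Baseline adjustment.** Let the raw-score SD be σ at both times and the baseline-to-4-month correlation be r. The change-score variance is 2σ²(1 − r) and the ANCOVA residual variance is σ²(1 − r²). Their ratio is (1 − r²)/[2(1 − r)] = (1 + r)/2. For r = 0.7 it is 0.85 and for r = 0.4 it is 0.70, so ANCOVA variance is 15% to 30% lower.

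**Sensitivity.** If 20 to 25 is instead the raw-score SD, with r from 0.3 to 0.7 and 378 per arm, the SE runs from about 1.1 to 2.2. Power for 5 points with no threshold is then 64% to 99% by t-test on change and 82% to 99.8% by ANCOVA. With a threshold it is 1% or less at 10 points and 50% at 5 points.

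**The case against.** The best defence has five parts.

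- **Scope.** The conditional sentence follows one on subgroups and could be read as limiting tests there only. That sentence lists treatment arm among its groupings, however, and the conditional sentence is unrestricted and introduces every test in the section. The narrow reading does not remove the problem.
- **Reporting.** A reader might infer that harm goes unreported. It does not. Descriptive results and mean changes are unconditional, a reader could rebuild an interval from means, SDs and numbers, and toxicity is assessed separately by CTCAE and its patient-reported version. This stands. What is missing is formal inference on the quality-of-life objective, and medians with interquartile ranges would not allow that reconstruction.
- **Error rates.** A reader might infer inflated type I error or p-values biased upward. Neither follows. Requiring a large difference before testing can only reduce false positives, and selection makes p-values smaller. The exaggeration belongs to estimates singled out for passing the threshold, not to the full set of reported means.
- **Baseline.** A reader might infer that baseline data are thrown away. The endpoint is a "change from baseline in global health status score) between the two arms", so baseline is used. In a 1:1 randomised trial the t-test on change is valid, and the remaining cost is efficiency.
- **Threshold.** The protocol states none, and the SAP may supply it, so its absence is not the fault. The figure of under 1% belongs to an assumed 10-point threshold with a true effect half that size, and cannot be quoted as a property of the plan.

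**Conclusion.** The point holds in a limited form. Section 17.3 sets a rule under which a real arm difference in global health status below an unstated threshold receives no formal inference, although quality of life is a stated secondary objective. How much is lost depends on the threshold. For a true 5-point deficit, with an SD of change of 20 to 25 and 350 to 378 per arm, the chance of a significant test falls from 75% to 93% to about 50% (5-point threshold) or under 1% (10-point threshold). A 3-point threshold costs almost nothing. A 4-point one costs about 5 to 8 percentage points at SD 25 and 17 to 18 at SD 20. The rule is thus close to harmless when the threshold sits near the significance limit, and costly when it sits well above it.

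The unadjusted t-test on change is a lesser matter: valid, but with more variance than a baseline-adjusted analysis. All the sizes rest on the stated assumptions; the finding about the rule does not. This is a free improvement, not a threat to the trial's primary conclusion.

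**What to change.** Delete the conditional sentence in section 17.3. State that the arm difference in QLQ-C30 global health status at 4 months will be estimated with a 95% confidence interval whatever its observed size, by ANCOVA or by a mixed model over the scheduled visits, adjusted for baseline score and the minimisation factors. Use the clinically important difference only to interpret the interval, and apply the same model to the other scales that have a baseline measurement.

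Reconcile the minimisation factors first. Section 9.5.2 lists multiple long-term conditions where section 16.1 lists perineural invasion; the other four factors agree.

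The cost is a wording change in the protocol, carried into the SAP, and a little analysis time. No new data are needed, since both measurements are already scheduled in both arms.

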17.4 Quintet Recruitment Intervention (QRI) and INCLUSION Study Within A Project (SWAP)

To address recruitment and inclusion challenges, we have integrated a Quintet Recruitment Intervention (QRI) (40), a mixed methods intervention developed to optimise recruitment and informed consent. A complementary 'Study Within A Project' (SWAP) (41) will be conducted alongside, to optimise inclusion of particular participant groups facing additional recruitment and retention challenges and develop methodological tools to promote inclusion more broadly during trial recruitment. This integrated study is referred to as QRI+INCLUSION.

The QRI comprises two iterative and overlapping phases (30). Phase 1 involves mixed methods data collection of screening data and qualitative data involving patients and professionals to gain a detailed understanding of the recruitment process. Phase 2 involves feedback of findings to the Chief Investigator and Trial Management Group, to agree tailored interventions to improve recruitment and informed consent. The SWAP will overlay an inclusivity lens on all QRI activity.

Phase 1

- Pre-trial workshops: QRI: Professionals' views will be explored in 2-3 workshops involving clinical co-applicants and recruiters at collaborating sites to facilitate exploration of patient screening/identification pathways, eligibility criteria and equipoise. This work is covered by a separate Research Ethics Committee (REC) approval (University of Bristol, Faculty of Health Sciences Research Ethics Committee).
- Mapping of screening, eligibility, and recruitment pathways, which will help to identify where patients are lost from the recruitment pathway, including those from under-served groups e.g., non-English speaking, capacity to consent, or where geographical or deprivation factors may have affected recruitment.
- Patients will be invited to consent to the recording of all conversations during which participation in the trial is discussed.
- Professional and patient interviews, with purposive sampling to investigate reasons for losses to recruitment and explore experiences of under-served groups and potential barriers to inclusion.
- A QuinteT researcher will observe all TMG and TSC meetings during which the study protocol and patient facing paperwork is developed and finalised, with a focus on discussion and final presentation of equipoise and eligibility criteria.

Phase 2

Findings from phase 1 will be presented to the CIs and TMG. If recruitment difficulties are evident across the trial or at particular sites, the CI/TMG and QuinteT team will agree actions to improve recruitment and information provision. The specific actions implemented will be grounded in the

findings from analysis of the data above, with format dependent on the nature of the recruitment barriers identified and may include feedback to individual recruiters, study wide feedback or amendments to recruitment pathways.

17.4.1 Consent processes for the QuinteT Recruitment Intervention

a) Health care professional consent

Recruiting staff and TMG member consent will be obtained through a 'master' consent form that covers all aspects of the QRI. The consent form will set out individual clauses, with the option to select 'Yes' or 'No' for each research activity accordingly. Site team coordinators or the QuinteT researcher will obtain written consent from all relevant site staff. This will be a one-off process to cover consent for all future recordings of appointments, interviews, and observations of TMG/investigator meetings throughout the study.

b) Patient consent

Audio recording/observing recruitment appointments:

Patients will be sent a copy of the PIS in advance or given the PIS in an initial face to face discussion. Patients will be provided with sufficient time to read the information, ask any questions, and consider participation in the QRI/Information study, which involves consenting to the audio recording of discussions about the study and/or a qualitative interview with the QRI researcher.

A flexible one or two-step consent process will be offered for capturing consent to audio-recording initial discussions about potential participation in the SCC-AFTER study.

- 1) One step: where patients have had the PIS sent in advance, site team members will invite a decision on participation in the QRI/information study and collect consent using approved consent processes to audio record the recruitment discussion and take part in a qualitative interview respectively.
- 2) Two step: where patients have not previously seen the SCC PIS, site team members will invite spoken consent to audio record the conversation about the study at the very start of the recruitment consultation. At the end of this conversation, patients will be asked to confirm whether they wish to follow up spoken consent with approved consent processes. Patients will be able to provide consent using approved processes at the end of this consultation or at a later date. Future discussions about potential SCC-AFTER participation will be audio-recorded subject to receiving this consent; if patients choose not to provide consent, the recording made from their initial discussion will be deleted, and no further recordings made.

All approved consent processes for the QRI/Information study will mirror those described for the main trial (see section 9.4) with the aim of optimising inclusion in the QRI + INCLUSION study.

Interviews

Patients will receive information about the interview processes in the PIS and will be able to provide consent using approved consent processes to take part in an interview at the same time as giving consent to audio recording of the recruitment consultation as described above. The QRI consent form will give the option to decline the QRI+INCLUSION study, consent to only the audio recording of recruitment consultations or only the interview, or consent to both.

17.4.2 QRI + INCLUSION Data Analysis

Screening and enrolment logs

The QuinteT researcher will analyse data using the Screened, Eligible, Approached, randomised (SEAR) (31) framework to observe differences between sites in recruitment patterns as new sites open. Simple descriptive analyses will identify points in the recruitment pathway at which patients are lost to recruitment to the cohort or trials and the reasons why. Detailed screening, eligibility, approach, and recruitment pathways will be compiled for sites, noting the point at which patients receive information about the study, which members of the clinical team they meet, and the timing and frequency of appointments. Recruitment pathways will be compared with details specified in the trial protocol and pathways from other sites to identify practices that are potentially more/less efficient. Numbers of screened, eligible, approached, and recruited patients will be compared across sites and considered in relation to estimates specified in the grant application/study protocol. Additional analysis of screening logs will focus on key non-identifiable demographic and health data recorded from medical records relevant to under-served groups. These data will drive the purposive sampling of and be triangulated with the qualitative data findings (see below) to identify barriers and potential solutions to recruitment.

Recordings of recruitment conversations and interviews with patients and healthcare professionals

Audio recordings of recruitment conversations will be sought from a purposefully sampled range of recruiting sites (showing higher and lower recruitment and including those agreeing to and declining to participate) to ensure maximum variation and recordings will be analysed by the QuinteT researchers.

The audio recordings will be used to explore information provision, management of patient treatment preferences, and randomisation decisions to identify recruitment difficulties and improve information provision. Audio-recorded recruitment consultations will be subjected to targeted transcription with relevant sections first identified then transcribed and identifying data removed before fuller analysis. Analysis will employ content, thematic, and novel analytical approaches, as described in the QuinteT recruitment intervention protocol (30).

Those declining participation within the trial and consenting to the QRI will be invited to take part in an interview to investigate their experiences of being given information about the trial and their understanding of trial information. Participants will be purposively sampled to include potential participants across a range of trial sites, with those who decline the study or those who accept participation then immediately decline the allocated intervention being prioritised for interview.

Healthcare professionals involved in recruiting patients to the study or working within the trial site teams to support recruitment may also be invited to take part in an interview to investigate their experiences of trial recruitment processes.

The screening, eligibility, approach and recruitment challenges relating to under-served groups identified in the previous QRI Phase 1 activities will inform the sampling of patients to explore their experiences of being approached about participation and of healthcare professionals to explore their views on factors impacting on inclusion of these groups.

All interview data will be analysed thematically using constant comparative approaches derived from Grounded Theory methodology (42) and triangulated with findings from analyses of SEAR data and analyses of audio recorded recruitment discussions where available.

Findings from the investigation of recruitment to SCC-AFTER will be fed back to the CI and TMG, where appropriate, to determine actions to optimise recruitment to the trial. Actions may include feedback to individuals or in groups as appropriate and will include template patient pathways, individualised or generic 'tips' sheets for recruiters and delivery of recruiter training.

The INCLUSION SWAP will triangulate the findings from the screening and recruitment logs, interviews and recruitment conversations using an inclusivity lens to enable conclusions to be drawn about the barriers to the recruitment of groups such as people with MLTC and/or other exclusionary factors. This will be included in the 'tips' sheets and other guidance and feedback as appropriate.

